# **12.1 General information**

Termination of pregnancy (TOP) is the commonest gynaecological procedure. It can be performed surgically or medically as described in section 1 (Background).

Vaginal bleeding and mild abdominal pain are normal post surgical and medical procedure. Nausea, vomiting and diarrhoea may also be experienced. There is also a risk of infection. Pain relief and antibiotics are provided as part of normal care [7]. Occasionally abortion is incomplete and surgical evacuation is required. Major complications of surgical termination are rare, but include uterine perforation, pelvic sepsis and haemorrhage.

Misoprostol is widely used in the UK to induce medical abortion and in cervical preparation for surgical termination, even though this is an unlicensed indication. Therefore for the purposes of this study misoprostol will be treated as an investigational medicinal product (IMP).

The Summary of Product Characteristics for mifepristone is included in the appendices. This will be prescribed and administered as per normal practice.

# **12.2** Use within the study

Misoprostol will be presented as 200µg tablets; packaged and labelled as an IMP.

### Surgical termination

Women will be admitted to the Surgical Day Unit where they will receive misoprostol  $400\mu$ g vaginally 3 hours prior to the estimated time of surgery [7]. Following induction of general anaesthesia and mechanical dilatation of the cervix, the uterus will be evacuated using vacuum aspiration with a 9-12 mm curette.

In the absence of excessive bleeding or other problems, women will be discharged 1-2 hours after the procedure.

In line with RCOG recommendations [7], surgical termination will only be performed after 6 weeks' gestation because of the high failure rate (relative risk 2.9 at very early gestations). The appointment for surgical termination will be timed in line with this recommendation.

### **Medical termination**

At an initial appointment participants will be given mifepristone 200mg orally on the Gynaecological ward by the nursing staff. After 36-48 hours, they will be admitted to the Gynaecological ward where they will receive misoprostol 800µg vaginally at approximately 8:30 a.m.

Following administration of misoprostol, participants will receive oral paracetamol (500mg) plus dihydrocodeine (10mg) or diclofenac (75mg), or parental diamorphine (5mg) as required and as per normal practice.

At the time of the termination participants will receive rectal metronidazole (1g), followed by oral doxycycline (200mg) daily for 7 days, commencing on the day of the termination.

In the absence of excessive bleeding, participants will be discharged 1-2 hours after passage of the uterine contents.

Subsequent management will depend on gestation period:

Less than 9 weeks

• If the contents of the uterus have not been passed 4 hours after misoprostol administration,

a second dose of misoprostol (400µg) will be administered vaginally or orally (depending on preference and amount of bleeding) [7].

• Subsequently, if abortion does not occur and bleeding is not excessive, women will be routinely discharged between 4:30 & 5:00 p.m. The abortion occurs at home and women return for follow-up after 2 weeks.

9 to 13 weeks

- If the contents of the uterus have not been passed 3 hours after misoprostol administration, further doses of misoprostol (400µg) will be given vaginally (or orally if bleeding is heavy) at 3 hour intervals up to a maximum of 4 further doses [7].
- If the contents are still not passed, an ultrasound scan will be performed. In cases of an ongoing pregnancy, missed or incomplete abortion, surgical evacuation will be performed.

# **13 RANDOMISATION**

Participants with a procedure preference will decide whether to opt for a medical or surgical termination.

Participants with no preference, and willing to be allocated a procedure at random, will be randomised using a computer system with web-based access for trial personnel (PowerTrial). Randomisation will be stratified according to gestation (less than 9 weeks and between 9 & 13 weeks) and for previous termination of pregnancy.

# 14 STUDY DATA

# 14.1 Data collection

Baseline demographic data, including medical history and method of any previous termination, education level, occupation and income will be collected by the nurse practitioner or research nurse for all participants. Contact details (including where possible mobile phone numbers) and availability will also be collected.

Those expressing a procedure preference at baseline will be asked to nominate one or more reasons from a list of eight, developed as part of the pilot trial:

- 1. General anaesthetic (GA) want to be asleep (PS)
- 2. Fear of GA or desire to be awake and in control (PM)
- 3. Fetus do not want to see fetus (PS)
- 4. Pain perceived medical as more painful (PS)
- 5. Visits to hospital wanted minimum (PS)
- 6. Duration of procedure less time in hospital (PS)
- 7. Previous experience (i.e. had prior TOP) PM or PS
- 8. Other (<5% of responses)

All participants will be invited to return for an out-patient (hospital or community clinic) assessment 2 weeks after the procedure. Outcome data will be collected at 2 weeks (by interview and questionnaire) and at 3 months (by questionnaire) after the procedure. For women who do not attend their visit for 2 week follow up, collection of outcome data will be attempted where previously agreed via telephone interview, mobile text message & postal or web-based questionnaire. All visits and telephone interviews will be conducted by a research nurse.

Acceptability - This will be determined at 2 weeks and 3 months after the procedure by responses to the closed question 'If you ever have another termination of pregnancy, would you opt for the same method?'. This simple question has been used in previous preference

trials of TOP [14, 15] and can, if necessary, be easily determined by phone, questionnaire or text message.

Strength of preference - To measure women's strength of preference for medical or surgical termination we will measure willingness to pay. This technique is being increasingly used in health technology assessment [32] and has been used previously for assessing strength of preference for abortion method [23, 33]. Interviews will be conducted, using the payment card method [34], in all women in the preference arm prior to the procedure where they will be asked to state their maximum 'willingness to pay' amount for the termination method they have chosen. Interviews will also be conducted on all women in both the randomised and preference arms at 2 weeks after the procedure when they will be asked to state their maximum 'willingness to pay' amount to receive their preferred option at a future date. The validity of women's responses will be tested by examining the correlation between stated 'willingness to pay' and level of income.

Satisfaction with care - The methodological pitfalls of measuring satisfaction with care have been reviewed recently [35]. Women will be asked to rate the quality of care during the termination and the counselling and support afterwards using a 5 point Likert scale (from excellent to poor) at 2 weeks and 3 months after the procedure. Measures in which patients are asked to rate the quality of aspects of their care show greater response variability than measures which seek direct ratings of satisfaction [36] and are better predictors of whether patients will return to the same doctor in the future [36]. For analysis we will distinguish those who rate their care as excellent from the remainder as this provides better discrimination [37]. A similar assessment has been used in our pilot trial. Ratings of care will be supplemented by information on satisfaction with care from the qualitative study.

Experience of care - To provide information about the reasons underlying acceptability judgements, we will use a semantic differential rating technique administered at 2 weeks and 3 months post procedure. This instrument uses a pair of opposite adjectives (for example painless-painful) as endpoints on a graphic Likert scale. Women will be asked to indicate their experience by placing a mark on the scale. Twelve bipolar adjectives will be used, scored along an evaluation dimension representing a positive or negative attitude ranging from 3 to -3. Rating scores are quick and easy to complete and have been used previously to measure attitude towards termination of pregnancy [14,38].

We plan to undertake a further analysis to explore the relationships between willingness to pay, satisfaction and acceptability measures.

Distress, anxiety and depression - Distress will be measured using the IES at 2 weeks and 3 months after the procedure. This 15 item scale measures subjective distress to a specific event (in this case termination of pregnancy) [39] and is the most likely to pick up a difference in actual experience of having one procedure rather than another. Two subscales measure intrusion and avoidance and both are likely to arise differently from the procedures under comparison. Anxiety and depression will be measured using the HADS at 2 weeks and 3 months after the procedure. This is a widely used 14 item self report scale designed for medical patients [40]. Depression is the main problem service providers have been concerned about [21]. Both the IES and HADS have been used in women after termination of pregnancy [21-23] and in our pilot study.

Quality of Life (EQ-5D) – This is a six itemed validated questionnaire developed by a European committee to provide a preference-based measure of quality of life, needed for the economic evaluation [41].

Emergency admission - Efficacy will be determined by comparing the rates of emergency admission (on the day of the procedure or after discharge) at 2 weeks and 3 months after the procedure. All women will be questioned about adverse events at the 2 week and 3 month follow up to ensure that data is also captured for admissions or visits to another hospital or their GP. The rationale for choosing this outcome is that it is likely to include all women with significant procedure-related morbidity due to (a) incomplete abortion, missed abortion or ongoing pregnancy (all of which require surgical evacuation) and (b) pelvic infection without retained products of conception. Further there is evidence to suggest that women experiencing a failed termination (requiring surgical evacuation) or excessive pain and/or bleeding (resulting in admission) are more likely to classify the experience as unsatisfactory [42] and to opt not to have the same procedure again in the future [20, 42].

Frequency and extent of symptoms - The incidence of nausea, vomiting, diarrhoea, dizziness and abdominal pain on the day of the procedure will be recorded as well as an assessment of the severity of pain (using a 10 cm visual analogue scale) and analgesic use. Symptoms after discharge will be ascertained at the 2 week follow up visit by the research nurse. Specifically the duration and severity of vaginal bleeding and pain as well as the length of time taken off work and to return to normal activity will be recorded [15].

Concomitant medications will be recorded at baseline and at the time of the termination procedure by abstraction from the medical notes. Women will be asked about concomitant medications at 2 week follow up.

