#### Protocol ID: TOP/SCR/002

gestational age [14, 15]; early in pregnancy women appear to perceive the medical procedure as easier and more natural while later it is perceived as more stressful (related to concerns about pain and seeing the foetus) [16-18]. If a woman has a preference for one method she is unlikely to be enrolled in a randomised trial or she may refuse the allocated method [17]. To represent the full range of service users, randomised trials need to include preference arms.

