### **Primary objectives**

To determine the acceptability of medical and surgical termination procedures as determined by their preferred method for any future TOP.

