#### **Primary outcome measures**

The primary outcome variable is acceptability of the procedure at 2 weeks after the procedure; participants will be asked if they would have the same method of termination again.

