## **15** STATISTICAL CONSIDERATIONS

# **15.1 Statistical analysis**

The analysis strategy will be similar to that used in a partially randomised preference trial of treatment for depression [43]. The trial will contain 4 intervention groups:

- 1 randomised to medical termination (RM)
- 2 randomised to surgical termination (RS)
- 3 preference for medical termination (PM)
- 4 preference for surgical termination (PS)

The analysis will be on an intention to treat basis (although it is anticipated that women will always get the randomised or preferred intervention). Those in either medical arm (RM or PM) who subsequently receive surgical intervention, due to incomplete or missed abortion, will be analysed as per the assigned medical arm.

Baseline variables - Although randomisation should balance out baseline characteristics, it will be important to compare these in the four groups to see if those who are prepared to be randomised differ from those who have a preference. If so, there are problems in extrapolating any conclusions from the randomised arms to the general population.

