# Appendix B: Willingness to Pay

### **Methods and Questions**

Women will be asked to state their WTP for their preferred method of termination at the following points

1. Pre TOP – for women expressing a preference and enrolled in the 'preference arm' we will ascertain the maximum amount WTP using the payment card method

2. Post TOP – all women who underwent TOP will be asked which method they would choose if undergoing a future TOP and IF they would be WTP an amount to receive that preferred option at a future date. If they answer 'yes' to this we will ascertain the maximum amount WTP using the payment card method

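### The primary item asks about the same method without naming it, so the answer is ambiguous for medical-arm women who go on to surgical evacuation

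*Protocol*

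**What the plan says.** The Protocol describes the primary endpoint in two ways.

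- **Objective.** Section 8 defines acceptability "as determined by their preferred method for any future TOP". The summary in section 5 agrees.
- **Instrument.** Section 9 says "participants will be asked if they would have the same method of termination again", at 2 weeks. Section 14.1 gives the closed question: "If you ever have another termination of pregnancy, would you opt for the same method". It may be answered by phone, questionnaire or text message.

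The arm in which each answer counts is fixed separately. Section 15.1 states: "The analysis will be on an intention to treat basis (although it is anticipated that women will always get the randomised or preferred intervention". It adds that medical-arm women who go on to surgery, "due to incomplete or missed abortion, will be analysed as per the assigned medical arm". Section 12.2 makes surgical evacuation part of the 9 to 13 week medical pathway when the pregnancy continues or the abortion is missed or incomplete.

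A named-method question exists elsewhere. Under Appendix B, all women after the procedure are "asked which method they would choose if undergoing a future TOP". That belongs to the willingness-to-pay interview, and no rule links it to the primary outcome.

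**The concern.** For most women the objective and the instrument coincide: each has experienced one method, and whether she would have it again reveals which one she prefers. They separate for a woman in a medical arm whose termination ended in surgical evacuation. She has experienced both methods, so *the same method* can mean either, and the Protocol does not say which.

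Two errors are possible:

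- She would choose surgery next time, reads *same* as surgery and answers yes. She is counted as accepting medical termination.
- She would choose medical again, reads *same* as surgery and answers no. She is counted as rejecting it.

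Surgical evacuation after a failed medical termination arises only in the medical arms, so errors from this source do not cancel between arms. At stake is the validity of a small part of the primary endpoint. A later analysis cannot recover what an unlabelled yes meant if no other answer from that woman is on record.

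**Working it through.** **1. Reproduce the design figure.** Inputs from section 15.2: 75% against 85%, significance level 5%, power 90%. Sidedness is not stated; two-sided is taken here. With the pooled-variance formula, no continuity correction and mean proportion 0.80:

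n = [1.96 × √(2 × 0.80 × 0.20) + 1.2816 × √(0.75 × 0.25 + 0.85 × 0.15)]² / 0.10²

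= (1.1087 + 0.7193)² / 0.01 = 334.2, rounded up to 335 per arm.

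This matches the Protocol. Power at 335 per arm is 90.1%, so the sample size is not at fault.

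**2. How many women are affected.** Section 7 gives:

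- 9 to 13 weeks: surgical evacuation in 0.9% (9-10 weeks) to 7.9% (12-13 weeks).
- Earlier: complete abortion in 98.5% and 96.7% in one source, so 1.5% and 3.3% not complete. The wider range of 95-97.5% gives 2.5-5% not complete.

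Of 335 medical-arm responders, 0.9% is about 3 women and 7.9% about 26. The upper rate applies only at 12-13 weeks. Section 7 puts terminations beyond 9 weeks at over 40% of the total. With an assumed 60/40 mix:

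- low: 0.6 × 1.5% + 0.4 × 0.9% = 1.3%
- high: 0.6 × 3.3% + 0.4 × 7.9% = 5.1%, which requires every later woman to be at 12-13 weeks.

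Something near 3% is a reasonable middle assumption.

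**3. Effect on the recorded proportion.** Let f be the evacuated share of the medical arm. Let a be the share of evacuated women who would choose surgery but answer yes meaning surgery, and b the share who would choose medical but answer no meaning not surgery. Then

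recorded medical acceptability = 75% + f × (a − b).

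Neither a nor b is in the documents. Setting b = 0 shows the loss of power if only false yes answers occur. Surgical acceptability is held at 85%, with 335 per arm, two-sided 5%:

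| f | a | Shift (points) | Difference (points) | Power |
|---|---|---|---|---|
| none | none | 0 | 10 | 90.1% |
| 0.9% | 50% | 0.45 | 9.55 | 87.5% |
| 3% | 25% | 0.75 | 9.25 | 85.6% |
| 2.5% | 50% | 1.25 | 8.75 | 81.9% |
| 5% | 50% | 2.5 | 7.5 | 70.2% |
| 7.9% | 50% | 3.95 | 6.05 | 53.1% |

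The last row applies the 12-13 week rate to the whole arm, so it lies beyond the plausible range. If b exceeds a, the sign reverses and the recorded difference is too wide.

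**4. Larger shifts.** A 2-point shift (77% against 85%) gives 75% power, and a 5-point shift (80% against 85%) gives 40%. At f = 3%, a 2-point shift needs a = 2/3. A 5-point shift needs almost every evacuated woman to misread even at f = 5.1% (5/5.1 = 98%). Evacuation does not plausibly produce the second case.

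**The case against.** The strongest reply is that evacuated women probably read the question as intended. Section 14.1 reports that women whose termination failed and needed evacuation are more likely to decline the same procedure in future. That suggests they take *same* to mean the procedure that failed. This stands, and it is the main reason to expect a small effect.

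Other points also carry weight:

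- The question was used in earlier preference trials. If the assumed 75% comes from such data, it already contains any misread answers. Section 15.2 gives no source for the 75%, so this is possible but not shown.
- Visits and telephone interviews are conducted by a research nurse, who can clarify. Text message is a last resort.
- The Appendix B answer is a cross-check for women interviewed at 2 weeks. It does not cover a woman who replies only by text.
- Below 9 weeks, some evacuations may follow the 2-week answer, which reduces the number affected.

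Coding could be left to an analysis plan, which is not shown. But no coding rule can tell what an unlabelled yes referred to.

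A reader might also infer that women who switch method after allocation add to the problem, since section 7 says of a woman with a preference that "she may refuse the allocated method". The documents do not support this. The remark concerns women who hold a preference, section 13 randomises only women without one, and section 15.1 anticipates that allocation will be followed. No crossover rate is given.

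**Conclusion.** The point holds as a limited ambiguity in the primary item. For medical-arm women who have surgical evacuation, the yes/no answer does not establish the endpoint defined in section 8.

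The affected share is about 1.3-5.1% of the medical arm under the 60/40 assumption. At 3% evacuated and a quarter answering yes meaning surgery, the shift is 0.75 points and power is about 86%. At 5% and one half, it is 2.5 points and about 70%. The misreading shares are assumptions, and both cases take false yes answers alone.

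A reader might conclude that the error always favours the medical arm and so always shrinks the difference. That is not established: false no answers are equally possible in principle, and the documents do not fix the net sign. The 335 per arm needs no change. This is a cheap improvement to the instrument, not a defect that undermines the trial.

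**What to change.** In sections 9 and 14.1, make the primary item a named choice: if she ever had another termination, which method would she choose, medical or surgical? Use it in every collection mode, including text message. Score the procedure as acceptable when the named method equals the assigned method (randomised groups) or the preferred method (preference groups), and state this rule beside the intention-to-treat paragraph in section 15.1. This brings the instrument into line with sections 5 and 8 and with the question in Appendix B.

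Keep the existing question alongside it, so that results can still be compared with the earlier trials that used it and so that disagreement between the two items can be counted in evacuated women.

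The cost is one extra short item and a one-line scoring rule. The change has to precede data collection, because an answer already given without a named method cannot be reinterpreted.

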### Secondary objectives

To compare experiences of care, strength of preference, psychological impact, efficacy and cost effectiveness of surgical versus medical termination.

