#### Secondary outcome measures

A secondary comparison of acceptability of the procedure will also be determined at 3 months after the procedure. Additional secondary outcome variables are strength of preference for the procedure, measured after 2 weeks; experiences of care, psychological impact, efficacy and satisfaction with care, measured at 2 weeks and 3 months after the termination procedure.

Further analysis will be performed to explore the relationships between willingness to pay, satisfaction and acceptability measures.

In order to better understand women's decisions regarding termination of pregnancy the study will include a qualitative component. A conceptual model of preferences will be developed via conjoint analysis in a group of non-pregnant women, and then explored via interview in a sample of women who have participated in the trial 2 weeks after their termination procedure.

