**Table of events** 

	Visit	1 (Baseline)	2	3	
	Time	up to -2w	0	+ 2w	+ 3m
Inclusion/exclusion screening		Х			
Written informed consent		Х			
Randomisation, if applicable		Х			
Reason for preference, if applicable		Х			
Demography		Х			
Medical history		Х			
Concomitant medication		Х			
Ultrasound		Х			
Strength of preference		X*		Х	
Termination procedure			х		
Adverse events			х	Х	Х
Concomitant medication			х	х	Х
Acceptability				х	Х
Satisfaction with care				х	Х
Experience of care				х	Х
Impact of Event Scale				х	Х
Anxiety & Depression Scale				х	х
Quality of Life (EQ-5D)				x	Х

x\* only determined prior to procedure in the preference group

Consent for Qualitative sub-study		Х	
Qualitative interview		х	

The study involves up to 3 hospital visits; the third visit is currently only part of normal care for those patients where it is unclear if medical abortion has been complete or who are experiencing problems. However the RCOG has recently recommended that all women should be offered a follow-up appointment within 2 weeks of abortion [7].

Alternative methods of collecting the primary and secondary outcome data will be discussed at baseline to ensure maximum follow up:

- The third visit can be performed in a community clinic (based within Sexual & Reproductive Health Services), rather than the hospital setting.
- If participants fail to attend the 2 week follow up visit, contact and data collection will be attempted by telephone or by postal questionnaire (with an option to complete the questionnaire via the internet), according to their consent. Also if agreeable, a final option of text message will be used to elicit primary outcome data; text messaging may also be used for a visit reminder.
- 3 month follow up data will be collected via postal or web-based questionnaire.

From month 10 of recruitment, 32 women (8 from each arm) will be invited to join the qualitative sub-study during the 2 week follow up contact. A convenient time will be arranged by the researcher to perform this interview.

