#### Secondary analysis

Secondary comparison of medical and surgical arms (preference and randomised subgroups combined):

- a. Comparison of proportions of women finding the procedure acceptable and rating the quality of care as 'excellent' the comparison will adjust for key baseline variables using logistic regression. We will also investigate the interaction between past history of TOP and intervention group on acceptability, and gestational age (as a continuous variable) and intervention group on acceptability.
- b. Comparison of mean values of psychological and rating scales the comparison will adjust for key baseline variables using multiple regression.
- c. Comparison of proportions of women with emergency admission and particular symptoms the comparison will adjust for key baseline variables using logistic regression.
- d. Comparison of WTP between those women in the combined groups.

Tertiary comparison of combined preference and randomised groups:

The aim of this comparison is to determine if receiving a preferred intervention improves key outcomes. Comparisons will be of acceptability, psychological and rating scales with methods as for secondary comparisons.

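### HADS has no baseline, so existing anxiety and depression cannot be directly adjusted for in the two non-randomised comparisons; the randomised comparison loses only precision

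*Protocol*

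**What the plan says.** The secondary objectives (protocol section 8) are "To compare experiences of care, strength of preference, psychological impact, efficacy and cost effectiveness of surgical versus medical termination". Section 9 lists among the secondary outcomes "experiences of care, psychological impact, efficacy and satisfaction with care, measured at 2 weeks and 3 months after the termination procedure". Section 14.1 repeats this timing for each instrument: "Distress will be measured using the IES at 2 weeks and 3 months after the procedure" and "Anxiety and depression will be measured using the HADS at 2 weeks and 3 months after the procedure". In the table of events the row "Anxiety & Depression Scale" is marked only at 2 weeks and 3 months. The EQ-5D, which has an anxiety/depression item, is also scheduled only after the procedure.

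Before the procedure, section 14.1 provides: "Baseline demographic data, including medical history and method of any previous termination, education level, occupation and income will be collected". The table of events adds concomitant medication, ultrasound and, for the preference group only, strength of preference. None of these measures mood.

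Section 15.1 uses the psychological scales three times:

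- Primary analysis, item b: means are compared between the randomised arms.
- Secondary analysis, item b, with preference and randomised women combined: "Comparison of mean values of psychological and rating scales the comparison will adjust for key baseline variables using multiple regression".
- Tertiary comparison: preference v randomised women, by the same methods, to learn whether getting the method one prefers improves outcomes.

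On baseline characteristics, section 15.1 also says that "it will be important to compare these in the four groups to see if those who are prepared to be randomised differ"; the contrast is with the preference groups.

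**The concern.** In the second and third comparisons some or all of the contrast is between groups that selected themselves. Regression on baseline variables is the only protection. A HADS score taken before the procedure is the obvious covariate for a HADS score taken after it, and it will not exist. A difference at 2 weeks could then reflect who chose what, rather than what the method, or receiving the preferred method, did.

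The same gap limits the four-group baseline comparison. It can show differences in age, education or obstetric history, but not in existing anxiety or depression, which is the characteristic closest to this objective.

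This is a data-collection gap. A statistical analysis plan cannot supply a covariate that was never recorded, and for every woman recruited without it the opportunity is lost.

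**Working it through.** **The plan's own figure.** The only sample size (section 15.2) is for acceptability: 75% v 85%, 5% significance (taken as two-sided), 90% power. With pooled variance,

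n = [1.960 × √(2 × 0.80 × 0.20) + 1.282 × √(0.75 × 0.25 + 0.85 × 0.15)]² / 0.10² = 335 per arm after rounding up.

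This reproduces the stated 335 and is not in dispute. No figure is given for HADS.

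**Inputs from section 15.2.** 335 responders per randomised arm (670 in all); 50% of recruits have a preference; 40% are lost to follow-up. Applying the same loss to 1116 preference women gives 1116 × 0.6 ≈ 670 responders.

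**Assumptions not in the documents.** HADS SD 4; correlation r between baseline and follow-up of 0.3 to 0.6; equal SDs at both times; preference women split evenly between methods, giving 670 responders per pooled method, half of them randomised; a baseline gap of 1 point between the self-selected groups; no part of the gap removed by other covariates.

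**Standard errors.**

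- Randomised arms: 4 × √(2/335) = 0.309
- Pooled methods, or preference v randomised: 4 × √(2/670) = 0.219

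**Spurious difference if there is no true effect.** Where the whole contrast is self-selected, it is r × gap. In the pooled comparison the randomised half of each side has no expected gap, so it is 0.5 × r × gap.

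| r | Pooled medical v surgical | In SE | False-positive rate | Preference v randomised | In SE | False-positive rate |
|---|---|---|---|---|---|---|
| 0.3 | 0.15 | 0.7 | about 11% | 0.30 | 1.4 | about 28% |
| 0.6 | 0.30 | 1.4 | about 28% | 0.60 | 2.7 | about 78% |

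The false-positive rate is Φ(b/SE − 1.96) + Φ(−b/SE − 1.96), where b is the spurious difference; the nominal rate is 5%. The 1-point gap means preference-medical v preference-surgical women in the pooled columns, and preference v randomised women in the others.

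**Randomised arms.** Adjusting for baseline multiplies the variance by 1 − r²: 0.91 at r = 0.3, 0.75 at 0.5 and 0.64 at 0.6, a cut of 9 to 36%. At r = 0.5, 335 per arm is worth 335/0.75 = 447. Without adjustment the difference detectable with 90% power is (1.960 + 1.282) × 0.309 = 1.00 point. With it, this falls to about 0.96 (r = 0.3) or 0.80 (r = 0.6).

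**The case against.** The strongest reply is that the main comparison of psychological scales is the randomised one. It needs no baseline to be unbiased and, on the assumptions above, already detects about 1 point. The exposed comparisons are labelled secondary and tertiary and serve a secondary objective. This stands, and it limits the importance of the point.

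The IES is event-specific, and section 14.1 considers it the scale most likely to show a difference between procedures. A pre-procedure IES would not be an equivalent baseline, so the gap concerns HADS only. This also stands.

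A reader might infer from the Background (section 7) that anxious women choose one method. The text does not say so. It says that later in pregnancy the medical method is seen as more stressful, which is a view of the method tied to gestation. Gestation is measured by ultrasound, is a randomisation stratum and can enter the regression. A mood gap between the groups is therefore possible but not shown, and the 1-point gap is an illustration.

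Medical history, concomitant medication and previous termination are recorded and could remove part of any difference. They are weak proxies for current anxiety and depression, so this narrows the problem without closing it.

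A baseline HADS would itself be imperfect. Appendix F asks about the past week, so the score would partly reflect distress about the pregnancy, which could lower r. Under section 11, preference women confirm their choice at consent, so a score taken afterwards may already reflect having secured that choice. Adjusting for it could then remove part of what the tertiary comparison seeks. This stands and shapes the fix.

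**Conclusion.** The point holds as a limitation of the two non-randomised HADS comparisons. On the stated assumptions, a 1-point gap carries 0.15 to 0.30 points into pooled medical v surgical and 0.3 to 0.6 points into preference v randomised, against a standard error of 0.219. The second is the more exposed because nothing in it is randomised. The actual size depends on a gap and a correlation that the documents do not give.

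Three stronger readings are not supported:

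- That the randomised HADS comparison is biased for want of a baseline. It loses precision only.
- That the pooled comparison carries the full 0.3 to 0.6 points. Under section 15.2 about half of those pooled are randomised, which halves the carry-over.
- That existing distress cannot be addressed at all. It cannot be adjusted for directly, but partial proxies exist.

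The primary outcome and the sample size are unaffected. The change is worth making because it is cheap and cannot be made later.

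**What to change.** Add HADS to Visit 1 for all participants, in the table of events (section 9) and in section 14.1. It should be completed after consent to take part, before randomisation and, where practicable, before a preferred method is confirmed. In section 15.1:

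- name it as a covariate for the HADS outcomes in item b of the primary analysis, item b of the secondary analysis, and the tertiary comparison;
- include it in the four-group baseline comparison;
- show the tertiary result adjusted and unadjusted side by side, because in preference women the score may follow their choice;
- use it to examine selective loss to follow-up. Section 15.2 assumes 40% loss, and the pilot in section 7 suggested lower follow-up in the surgical arm (95% confidence interval for the difference 2% to 31%).

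The cost is one 14-item self-report form at an existing visit, with no extra procedure. It adds a few minutes at a sensitive consultation, in a protocol that deliberately limits the burden on trial women, and some women would need interpreter help, since six languages besides English are eligible.
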